Screening, consent and randomization. Individuals who pass the telephone screening will be scheduled for a screening visit (SV) in the Geriatric Research Clinic (GRC) in the Sticht Center on Aging. Before any data collection, all participants will provide written informed consent and complete a HIPAA authorization form in accordance with the Wake Forest School of Medicine Institutional Review Board policies. DHP patients who pass the in-person telephone screen will be given the option of completing a prescreen visit (PSV; informed consent, MoCA, SPPB, and weight and height for BMI; see below) with the DHP recruitment coordinator at the DHP after their scheduled DHP care provider visit if time allows. If they are eligible following the prescreen visit, they will be scheduled for the full screening visit at the GRC.

Individuals who meet all eligibility criteria and provide informed consent will be invited back for the first baseline visit 1 (BV1). At the end of BV1, participants will be randomized to participate in the muscle biopsy substudy (those who are not on anti-coagulants) using a web-based randomization scheme (developed by [name]) with blocking by gender and race with a goal of achieving $n=32$ pre- and post-muscle biopsy samples. At the end of baseline visit 2 (BV2), participants will be randomized to one of the two study interventions (vitamin D₃ or placebo) using a web-based randomization scheme (developed by [name]) with blocking by gender, race, and muscle biopsy subgroup. Block size and the randomization sequences will be unknown to the research staff. Muscle biopsy and intervention assignment will be generated using a program that the study coordinator will access from her PC through the study website.

Schedule and organization of assessment visits

All assessments will be conducted during 5-6 visits according to the timeline in **Table 2**: 1 screening visit; 2 baseline visits; 1 or 2 (participants undergoing a muscle biopsy only) 4-month mid-intervention follow-up visits; and 1 12-month post-intervention follow-up visit. Assessments will take place in the Geriatric Clinical Research Unit, the Geriatric Research Clinic, or the Downtown Health Plaza (prescreen visit only).

Activity/assessment	Visit code	SV	BV1	BV2	On trial	4FV1	4FV2	12FV
		-3	-1	0		16	17	52

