Baseline visit 2 (BV2) will be conducted in the morning after an 8-hour fast in which participants will have blood drawn for analyses of serum 25(OH)D and 1,25(OH)D, plasma PTH, bioenergetic profiling (muscle biopsy subsample only), and blood for storage. For participants randomized to the muscle biopsy subsample, a muscle biopsy of the *vastus lateralis* (quadriceps) will also be taken. After vitals are collected and the blood draw (and muscle biopsy for those in the substudy) completed, participants will be given a snack. Participants in the muscle biopsy substudy will be given the option to continue with the BV2 visit following the muscle biopsy or to come back the following week to complete the BV2 questionnaires and be randomized in a separate visit. Then the Mobility Assessment Tool for Disability – short form (MAT-sf) to assess difficulty performing daily tasks, Digit Symbol Substitution Test (DSST) to assess attention and psychomotor speed, the Center for Epidemiologic Studies Depression Scale (CES-D) to measure mood and depression, and a sun exposure questionnaire (a modified version of the NHANES Dermatology Questionnaire) to estimate sun exposure and protection habits will be administered. At the conclusion of BV2, the study coordinator will check to see if the participant is randomized to receive either vitamin D₃ or placebo. The study coordinator will provide the participant with a 4-month supply of vitamin D₃ or placebo pills and monthly fall calendars to complete and provide oral and written instructions for taking the study supplement and completing the monthly fall calendars. Participants in the muscle biopsy substudy who do not elect to return the following week to complete the BV2 visit will receive a phone call 2-4 days following the procedure to check that they are not experiencing any adverse effects that may be related to the procedure (pain/soreness, signs of infection such as fever, excessive bleeding, or limitations in activity). The study physician ([name]) will be notified of any adverse effects related to the muscle biopsy procedure and any necessary action taken (e.g., follow-up visit scheduled with the study physician).

Monthly phone calls: Participants will be called once a month throughout the study to ensure they are taking and tolerating the supplements and completing the monthly fall calendars. The study coordinator will ask about any falls or adverse events that may have occurred.

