The first 4-month follow-up visit (4FV1) will occur during week 16 of the intervention. After an 8-hour overnight fast, participants will have their vitals taken and blood drawn for analyses of serum 25(OH)D and 1,25(OH)D, plasma PTH, metabolic panel, and storage followed by a snack. Lower extremity muscle power and strength, physical performance, grip strength, postural sway, stair climb, and gait velocity will be measured. The CHAMPS Physical Activity Questionnaire, MAT-sf, arthritis and joint pain questionnaire, and sun exposure questionnaire will be administered. Any changes to medical history and current medications and

dietary supplements will be reviewed. The first four months of fall calendars will be collected and reviewed. Participants will return the study supplement bottle with any remaining pills and an 8-month supply of vitamin D₃ or placebo pills will be provided to them to last through the end of the study. Instructions for taking the study supplement and completing the monthly fall calendars will be reviewed. Participants in the muscle biopsy substudy will be scheduled for their follow-up muscle biopsy and given oral and written instructions to prepare for the procedure. Following the 4-month follow-up visit, the study coordinator will check the lab results to determine if the 25(OH)D concentrations are at or above 30 ng/mL in participants randomized to receive vitamin D₃. Participants randomized to vitamin D₃ who have not achieved 25(OH)D concentrations \geq 30 ng/mL at the 4-month follow-up visit will be instructed to take 2 pills/d (4000 IU) for the remainder of the study. The study coordinator will also check to ensure that serum calcium levels are \leq 10.6 mg/dL. If a participant's serum calcium is $>$ 10.6 mg/dL at 4FV1, the protocol to assess whether the participant is hypercalcemic outlined in the Human Subjects Protection section (p. 10) will be followed.

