Participants will be randomized to either 2000 IU/d of vitamin D₃ or placebo for 12 months. The vitamin D₃ supplements and matching placebo pills will be manufactured by Tishcon Corp (Salisbury, MD). The proposed dose is expected to increase 25(OH)D concentrations by \sim 14 ng/mL.^{20,21} Previous vitamin D supplement dosing studies have observed a plateau in the increase in 25(OH)D concentrations in 6 to 8 weeks.^{20,22,23} In a recent dose-response study, a vitamin D₃ dose of 1600 IU/d increased 25(OH)D concentrations from $<$ 20 ng/mL to \geq 30 ng/mL over 1 year in 97.5% of participants.²⁴ However, we will measure serum 25(OH)D at the 4-month visit and increase the vitamin D₃ dose to 4,000 IU/d in participants in the intervention group with 25(OH)D concentrations $<$ 30 ng/mL (for every participant in the intervention group that has to increase their vitamin D₃ supplement dose to 2 pills/d after the 4-month follow-up visit, a random participant from the placebo group will also be instructed to take 2 placebo pills/d). Supplements will be dispensed at baseline and at the 4-month visit. Participants will be instructed to maintain their regular dietary intake and typical physical activity level and instructed to refrain from starting any other dietary supplements or changing the frequency/dose of any supplements they are currently using during the study. A brown bag review will be done at each visit of all

dietary supplements participants are currently taking; and the brand and type, frequency, and dose of vitamin D and calcium will be recorded on the medication inventory. Supplement adherence will be monitored monthly via phone calls and the remaining supplement pills counted at the 4- and 12-month visits. Since the half-life of 25(OH)D is ~2-3 weeks,²⁷ occasional missed pills should have a minimal effect on 25(OH)D concentrations. The neuromuscular function assessments, mechanistic studies of the muscle biopsy sample, and assessments of 25(OH)D and 1,25(OH)₂D will be conducted by study staff and investigators blinded to the vitamin D intervention assignment.

Outcome measures

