All data are obtained for research purposes only. Confidentiality of data is maintained by using research identification numbers which uniquely identify each individual. Data will be used only in aggregate and no identifying characteristics of individuals will be published or presented. The information collected has a low potential for abuse because the data do not address sensitive issues. Nevertheless, appropriate measures are taken to prevent unauthorized use of study information. Research records are kept in a locked room. Data access will be limited to study staff. Information linking IDs to individuals is kept on a secure, password-protected server to which only authorized study personnel will have access. Data and records will be kept locked and secured, with any computer data password protected. A web-based data entry system will be

created for this study which will allow access only to study staff (user id and password required to access). Blinded staff will not have access to blinded study information on the web-based database. Computer files are stored on file servers, which are backed up each night and stored for easy retrieval in case of emergency. Files may not be obtained from the research unit by persons other than the research personnel, who are asked to sign a document agreeing to maintain the confidentiality of the information. No data files distributed for analysis will include personal information. No reference to any individual participant will appear in reports, presentations, or publications that may arise from the study. After the study is completed, the data will be stored with other completed research studies in a locked secure area.

Data and Safety Monitoring

The principal investigator will be responsible for the overall monitoring of the data and safety of study participants. The principal investigator will be assisted by other members of the study staff. A Data Safety Monitoring Board (DSMB) has been established by the NIH, with responsibility to monitor all aspects of the study, including those that require access to any blinded data. The operational plan and all members were approved by the NIH Program Scientist. The NIH-appointed DSMB responsibilities are to:

- review the research protocol, informed consent documents and plans for data safety and monitoring;
- advise the NIA on the readiness of the study staff to initiate recruitment;

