- evaluate the progress of the trial, including periodic assessments of data quality and timeliness, recruitment, accrual and retention, participant risk versus benefit, performance of the trial sites, and other factors that can affect study outcome;
- consider factors external to the study when relevant information becomes available, such as scientific or therapeutic developments that may have an impact on the safety of the participants or the ethics of the trial;
- review study performance, make recommendations and assist in the resolution of problems reported by the Principal Investigator;
- protect the safety of the study participants;
- report to NIA on the safety and progress of the trial;
- make recommendations to the NIA, the Principal Investigator, and, if required, to the Food and Drug Administration (FDA) concerning continuation, termination or other modifications of the trial based on the observed beneficial or adverse effects of the treatment under study;
- ensure the confidentiality of the study data and the results of monitoring; and,
- assist the NIA by commenting on any problems with study conduct, enrollment, sample size and/or data collection.

The PI, co-investigators and the biostatistician will meet regularly to review study progress and to examine reports of adverse incidents as well as participant recruitment and follow-up. All *serious* adverse events will be reported to the Institutional Review Board (IRB) and if the event occurred as a direct result of participation in this study, an amendment will be made to the consent form and the PI will request new IRB approval. The PI and the Medical Director will meet quarterly, or as needed, to review all reported events.

Adverse events include any event that occurs during the course of the study that results in a participant suffering physical or mental injury, pain or suffering. Adverse events can be major, such as a subject who suffers cardiac arrest during neuromuscular function testing, or minor such as a subject pulling a muscle during neuromuscular function testing. This includes any events occurring while a subject is enrolled in the study, even if the event did not occur while s/he was actively participating in the activities called for in the research protocol. Deviations from the study's protocol are also considered an adverse, unexpected, or notable event and will be reported to the PI.

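### The study coordinator learns each participant's arm and also asks about falls and adverse events every month, so that collection is not blind to arm in a trial described as double-blind

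*Combined protocol and SAP*

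**What the plan says.** All references are to the combined protocol and SAP.

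- **Screening, consent and randomization:** "Muscle biopsy and intervention assignment will be generated using a program that the study coordinator will access from her PC through the study website".
- **Baseline visit 2:** when the visit ends, "the study coordinator will check to see if the participant is randomized to receive either vitamin D₃ or placebo". The coordinator then hands out the pills. No coded bottle is described.
- **First 4-month follow-up visit:** afterwards, the "study coordinator will check the lab results to determine if the 25(OH)D concentrations are at or above 30 ng/mL in participants randomized" to vitamin D₃. Those below the threshold move to two pills a day.
- **Vitamin D intervention:** for each such participant, "a random participant from the placebo group will also be instructed to take 2 placebo pills/d".
- **Monthly phone calls:** "The study coordinator will ask about any falls or adverse events that may have occurred".

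The blinding statements cover other work. The Vitamin D intervention section says that the neuromuscular tests, the biopsy studies and the vitamin D assays "will be conducted by study staff and investigators blinded to the vitamin D intervention assignment". Outcome measures repeats this for a list of study outcomes. Neither list contains falls or adverse events. Confidentiality and Privacy adds "Blinded staff will not have access to blinded study information on the web-based database", without saying which roles are blinded.

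Objectives and Experimental Overview both call the trial double-blind, and neither says whom the term covers.

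**The concern.** A caller who knows the arm can, without meaning to, probe harder or record more readily in one arm than in the other. Two kinds of data are exposed.

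- **Adverse events.** The definition in Data and Safety Monitoring extends to pain and suffering. Complaints of that kind depend more on how the monthly question is put than fractures, surgery or raised calcium do. Statistical Analyses specifies no between-arm comparison of adverse events. However, the NIH-appointed board may recommend continuing, stopping or modifying the trial "based on the observed beneficial or adverse effects of the treatment under study".
- **Falls.** These are exploratory, but they belong to Hypothesis 1 and are compared between arms by a Poisson GEE. They are the one outcome prompted by the coordinator that has a planned between-arm test.

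**Working it through.** No figure in the plan bears on this point, so there is none to reproduce. The check is a trace of roles, followed by a calculation of whether coded bottles alone would be enough.

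**1. Does the coordinator know the arm?** Yes, at three places: running the program, the check at baseline visit 2, and the month-4 check restricted to the vitamin D₃ arm. The last cannot be done as written without the arm.

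**2. Does the same role collect the data?** Yes, in the monthly calls.

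**3. Does any text undo this?** None was found. Keeping block size and sequence from staff protects future assignments, not one already made. The matched two-pill rule masks participants, not whoever applies it. The database rule does not place the coordinator among blinded staff.

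**4. Would coded bottles alone blind the coordinator?** From the documents: baseline 18 to <30 ng/mL, expected rise on active about 14 ng/mL, threshold 30 ng/mL, 136/2 = 68 per arm. Assumed: baseline uniform over 18–30; placebo mean change 0 or +3; SD of change 4 to 10 on active and 3 to 5 on placebo.

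For mean change m and SD s, P(below 30) = (1/12) ∫ from 18 to 30 of Φ((30 − b − m)/s) db. Write A for this probability on active and C on placebo.

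- Correct when guessing from a 30 ng/mL cut: ½[(1 − A) + C].
- If the two-pill rules are followed, anyone below 30 on one pill must be placebo, and so must anyone at or above 30 on two pills. With partners drawn at random, the share of the placebo arm identified is C(1 − A) + (1 − C)A.

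| SD active/placebo | Placebo mean change | A | C | Correct at cut | Placebo identified |
|---|---|---|---|---|---|
| 4/3 | 0 | 0.066 | 0.900 | 0.92 | 0.85 |
| 10/5 | 0 | 0.225 | 0.835 | 0.81 | 0.68 |
| 4/3 | +3 | 0.066 | 0.729 | 0.83 | 0.70 |
| 10/5 | +3 | 0.225 | 0.686 | 0.73 | 0.60 |

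Last row: ½[(1 − 0.225) + 0.686] = 0.73, and 0.686 × 0.775 + 0.314 × 0.225 = 0.60.

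So the month-4 result would usually give the arm away, at about 73–92% correct. This would affect the calls after month 4, 8 of 12. Bottle codes alone would protect only the first 4.

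**5. Would the two-pill list reveal the arm if the result were withheld?** It would hold equal numbers from each arm, but timing can separate them. Expected active participants on the list: 68 × 0.066 = 4.5 to 68 × 0.225 = 15.3. At 5–6 enrolled per month, 136 participants take 136/6 = 23 to 136/5 = 27 months. That gives 4.5/27 = 0.2 to 15.3/23 = 0.7 active additions per month, so a list is often one pair. The plan does not require the placebo partner to be at month 4. If the partner is not, the date of the instruction shows who is active.

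**The case against.** The strongest reply is that this is a recognisable design: one unblinded coordinator manages supply and the month-4 step, while participants and assessors stay masked. Much of that stands. Answers come from participants who learn their arm only at the end of the 12-month visit. Falls are first marked on participants' own calendars. Serum calcium is a laboratory value, and the history reviews and metabolic panels at months 4 and 12 give other routes to adverse events. What remains open is how events are asked about, probed and recorded, and how falls are prompted.

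The program might return only a bottle code, or several people might share the role. The documents say neither, and the arm-specific month-4 check argues against the first.

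It is also fair that the guessing figures do not measure harm. They test a coded-bottle scheme that the plan does not use, and they move with the assumed placebo change.

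A reader might infer that leg power and the other main outcomes are unblinded. The documents do not support this, since those assessments are assigned to blinded staff. A reader might also infer that recorded events distort those outcomes, because Statistical Analyses lets a review of health events decide which implausible values become missing. That route is possible but not shown.

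**Conclusion.** The point holds and should be addressed. Followed as written, the plan has adverse events elicited and recorded, and falls prompted, by a role that knows the arm, and the double-blind label is not reconciled with this. Confidence is high on who knows the arm and lower on the consequence. The bias cannot be sized from the documents, and its direction is unknown. It would be wrong to conclude that adverse-event or fall results will be biased by any stated amount.

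The 73–92% range rests on the assumed uniform baseline, SDs and placebo mean change of 0 to +3 ng/mL. It shows only that coded bottles would not be enough while the coordinator sees the month-4 25(OH)D result. Nor can the existing two-pill rule be relied on to hide the arm unless the timing of partners is controlled.

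**What to change.** 1. Have the existing web system return only an individual bottle code to the coordinator at baseline visit 2 and at the month-4 resupply. Release the arm after the 12-month visit forms are closed.
2. Send the month-4 25(OH)D result to the web system, or to existing data or statistical staff who have no participant contact. They issue the two-pill instructions under the rule already written, with each placebo partner drawn from participants at the same month-4 point, or in batches, so that timing does not show the arm. The coordinator still sees calcium and the metabolic panel.
3. Keep a documented emergency code-break route outside the coordinator.
4. Review implausible values with arm removed from the file.

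If the coordinator must stay unblinded, let existing staff who are blinded to arm and to 25(OH)D results make the monthly fall and adverse-event calls. State which roles double-blind covers.

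The cost is modest programming, individual bottle codes, up to 136 25(OH)D results reported separately from calcium (the same outside laboratory does both), and a short wait for the two-pill list. The system must hold the code-to-arm map, because the coordinator can no longer check it. The monitoring board's access to blinded data is unaffected. No dose or clinical rule changes.

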Age ≥ 65 to <90 years	Serious or uncontrolled chronic disease including: insulin-dependent diabetes; cancer requiring treatment in past year, except non-melanoma skin cancers; acute coronary event (within the last 6 months), uncontrolled angina, heart failure (stage 3-4), PAD, or stroke (within the last 6 months); uncontrolled hypertension (BP>200/110 mmHg); chronic respiratory disease requiring the use of oxygen; uncontrolled endocrine/metabolic disease; neurological (e.g., Parkinson's disease) or hematological disease; liver or renal dysfunction (eGFR <45 mL/min/1.73m ²); and musculoskeletal impairments severe enough to preclude functional testing
SPPB ≤ 10 if chair stand score is ≤ 3 or <10 if chair stand score is a 4	Evidence of impaired cognitive function (MoCA <18)
Initial serum 25(OH)D concentration of 18 to <30 ng/mL	Taking prescription vitamin D ₂ or taking >1000 IU/day of vitamin D ₃ (from all sources); taking an oral corticosteroid (i.e., prednisone at 7.5mg/d for 3 mos or equivalent); taking hormone replacement therapy
Not dependent on a walker	Inability or contraindications to consume daily vitamin D supplements (e.g., hypercalcemia, sarcoidosis, history of kidney stones in last 5 years)
Willing to provide informed consent and adhere to the protocol	Knee or hip surgery within the last 6 months or planned knee or hip surgery within the next year
Not involved in another behavioral, exercise, or investigational drug intervention study	Unwillingness to undergo a muscle biopsy

Inclusion Criteria	Exclusion Criteria
Self-reported physical performance difficulty	Weight loss of $\geq 5\%$ or more in the past 3 months
	BMI $> 40 \text{ kg/m}^2$
	Eye surgery (e.g., cataract surgery) within the past month or planned within the next month
	If the PI feels the participant is unlikely to follow the protocol

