height and weight) are collected and the blood draw completed, participants will be given a snack and continue with the remainder of the visit. First, the short physical performance battery (SPPB)¹⁵ will be administered and scored. If still eligible, participants will then undergo a cognitive screen (assessed using the Montreal Cognitive Assessment, MoCA¹⁶) and a medical history and review of medications and dietary supplements. A prescreen visit (PSV)* may be scheduled to assess eligibility on the SPPB and the MoCA. If this occurs, the participant will sign consent at the PSV and then weight and height will be obtained to calculate BMI and the SPPB and MoCA will be administered. If the participant qualifies, they will then be scheduled for the SV (and those measures would not be repeated again until follow up). The reason for doing a prescreen visit is those two measures will often disqualify someone from the study so it greatly improves our work flow and scheduling abilities to schedule this as a separate visit since the PSV can be done in the afternoon whereas the SV is a fasting visit and has to be done in the morning. Following the screening visit, the study coordinator will check the lab results to determine if the participant is still eligible based on blood work (25(OH)D between 18 and <30 ng/mL, liver and serum calcium within normal limits, and eGFR≥45). If the participant is eligible, they will be notified and scheduled for a baseline visit. If the participant is not eligible, they will be notified and given a copy of their screening blood work (if it was completed).

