- 2) Blood Draw. Participants may experience temporary pain, bruising, bleeding and a small risk of infection or fainting or dizziness during the blood sample collection process. Only trained staff will be responsible for the collection of blood samples.
- 3) Muscle biopsy. There may be some temporary discomfort and bleeding from the muscle biopsy. However, there is typically no discomfort felt during the procedure due to the use of lidocaine as a local anesthetic injected into the muscle. Temporary numbness of the skin near the sampling site can rarely occur. A small amount of bruising can also occur. There is a slight risk of bleeding into the tissue and infection, but this procedure is done under sterile conditions to protect against this. There is also a risk of a vaso-vagal response during or after this procedure, but there are trained medical personnel performing the procedure and a fully stocked crash cart is available should it be needed. To date, [name] and [name] have performed >600 muscle biopsies for aging-related research studies without a serious adverse event.
- 4) The risks of the vitamin D supplement intervention are minimal, but may include hypervitaminosis D. Although the proposed vitamin D₃ dose of 2000 IU/d is below the upper limit set by the Institute of Medicine (4000 IU/d), participants could exceed the upper limit if they begin consuming other vitamin D-containing supplements. Participants will be advised not to begin any new dietary supplements during the trial and of the possible side effects of hypervitaminosis D (e.g., non-specific symptoms such as anorexia, weight loss, polyuria, and heart arrhythmias; as well as increased serum calcium which can lead to vascular and tissue calcification including kidney stones). Those with contraindications to vitamin D supplements will be excluded (e.g., kidney impairment (eGFR <45 mL/min/1.73), hypercalcemia, sarcoidosis, and history of kidney stones). Serum calcium will be assessed at screening and at 4- and 12-month follow-up. Participants with hypercalcemia (serum calcium >10.6 mg/dL) at their 4-month visit will have a repeat serum calcium drawn within 2 weeks, and, if confirmed, the study supplement will be discontinued; however, we will continue following participants with confirmed hypercalcemia for outcomes.

Confidentiality and Privacy

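### The month-4 step-up to 4000 IU/d has no calcium condition, so a participant with an unresolved calcium above 10.6 mg/dL would be told to double the dose while the repeat is pending (minor, rare safety gap)

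*Combined protocol and SAP*

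**What the plan says.** The step-up rule appears twice.

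- **Schedule and organization of assessment visits, 4FV1 paragraph:** a vitamin D participant who has not reached 30 ng/mL "will be instructed to take 2 pills/d (4000 IU) for the remainder of the study".
- **Vitamin D intervention:** the study will "increase the vitamin D₃ dose to 4,000 IU/d in participants in the intervention group with 25(OH)D concentrations" below 30 ng/mL. For each such participant, a randomly chosen placebo participant is also moved to 2 pills a day.

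The 4FV1 paragraph then adds the calcium check: "The study coordinator will also check to ensure that serum calcium levels are" at or below 10.6 mg/dL. A higher value is referred to the Human Subjects Protection section. There, Potential Risks item 4 says that a participant above 10.6 mg/dL at the 4-month visit "will have a repeat serum calcium drawn within 2 weeks, and, if confirmed, the study supplement will be discontinued".

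Entry to the trial is handled differently. The screening paragraph requires the 25(OH)D range together with "liver and serum calcium within normal limits" before a baseline visit is scheduled, and Table 1 excludes "Inability or contraindications to consume daily vitamin D supplements (e.g., hypercalcemia, sarcoidosis, history of kidney stones in last 5 years").

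**The concern.** Starting 2000 IU/d requires an acceptable calcium. Doubling to 4000 IU/d requires only a low 25(OH)D. The calcium check at 4FV1 sits beside the step-up rule and is not a condition of it. The procedure it triggers covers confirmed hypercalcemia and says nothing about dose while the repeat is outstanding.

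A participant with 25(OH)D below 30 ng/mL and calcium above 10.6 mg/dL at the same visit would therefore receive two instructions: take twice as much, and return for a repeat calcium. What is at stake is that participant's safety during the pending interval. The issue is raising the dose on top of an unresolved abnormal value that the plan treats as a contraindication at entry.

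**Working it through.** The plan gives no figure on this point to reproduce. The check is a comparison of the text, followed by simple arithmetic on exposure.

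**1. Is there a hold anywhere?**

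| Place | Trigger | Action | Calcium condition on dose? |
|---|---|---|---|
| Screening paragraph, Table 1 | Entry at 2000 IU/d | Eligible or not | Yes |
| 4FV1 paragraph | 25(OH)D <30 ng/mL | 4000 IU/d to end of study | No |
| Vitamin D intervention | 25(OH)D <30 ng/mL | 4000 IU/d, with placebo match | No |
| Potential Risks, item 4 | 4-month calcium >10.6 mg/dL | Repeat within 2 weeks; stop if confirmed | Only after confirmation |

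The Data and Safety Monitoring section gives general oversight and event reporting, with no dose-hold rule. Nothing holds the step-up during the pending interval.

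**2. Extra dose in the interval.** Extra intake is 4000 − 2000 = 2000 IU/d.

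- To the last permitted day for the repeat draw: 14 × 2000 = 28,000 IU (56,000 instead of 28,000).
- Adding an assumed turnaround of 1 to 5 days: at most 15 to 19 days, or 30,000 to 38,000 IU.
- Repeat drawn on day 1 with 1-day turnaround: 2 days, or 4,000 IU.

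The 15 to 19 days are therefore a maximum. If the 2 weeks run from the visit, the overlap is shorter still, because the step-up cannot begin until the 25(OH)D result is back.

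**3. Effect on 25(OH)D.** Inputs from Vitamin D intervention: a rise of about 14 ng/mL for 2000 IU/d and a half-life of 2 to 3 weeks. Assuming linear first-order kinetics, the added rise after d days is 14 × (1 − 0.5^(d/h)), with h = 21 or 14 days.

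- d = 14: 5.2 (h = 21) to 7.0 (h = 14) ng/mL.
- d = 19: 6.5 (h = 21) to 8.5 (h = 14) ng/mL.

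Starting below 30, the participant stays below 30 + 8.5 = 38.5 ng/mL. At the mean rise, ordinary participants are expected to reach 18 + 14 = 32 to just under 30 + 14 = 44 ng/mL. No unusual level is projected.

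**4. How many participants?** There are 136 / 2 = 68 per arm. The documents give neither the proportion who will be below 30 ng/mL at month 4 nor the rate of calcium above 10.6 mg/dL. I assume a calcium rate of 1% to 3%, independent of 25(OH)D, and show three assumptions for the first figure.

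| Basis for number below 30 ng/mL | Candidates | Expected overlap | Chance of at least one |
|---|---|---|---|
| Cited dose-response study reached target "over 1 year in 97.5% of participants"; 2.5% × 68 | 1.7 | 0.017 to 0.051 | 2% to 5% |
| Rise normal with mean 14 and assumed SD 3 to 7 ng/mL; baselines uniform over 18 to 30 | 2.6 to 10.5 | 0.026 to 0.32 | 3% to 27% |
| Assumed 20% below 30 ng/mL | 13.6 | 0.14 to 0.41 | 13% to 34% |

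Overlap is candidates × calcium rate; the last column is 1 − (1 − rate)^candidates. The first row borrows from a different dose (1600 IU/d) and a lower baseline (<20 ng/mL). Statistical Analyses expects response to vary with genetics, BMI, health status and adherence, so that row may be too low. Zero is the most likely count in every row, but none of these figures is a derived upper bound.

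**The case against.** The strongest reply is that the two checks stand in consecutive sentences, are made by the same coordinator in one review of results, and go to the same laboratory. An ordinary reader would let the safety procedure govern anyone with a high calcium. That may well be what happens in practice, but it rests on judgment: the dosing sentence is unqualified and nothing tells the coordinator to wait.

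Second, other safeguards exist: normal calcium at screening, monthly calls "to ensure they are taking and tolerating the supplements" and to ask about adverse events, and the stop rule. These limit the risk and justify calling the gap minor. None of them holds the increase.

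Third, a participant with a higher 25(OH)D and the same calcium stays on 2000 IU/d while the repeat is pending, so a hold for low responders alone may look selective. The answer is that the hold puts both on the same footing: each continues the current dose until the repeat is back. Whether to pause the supplement for everyone with a high first value is a separate choice.

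A reader might infer more than the text supports:

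- **That staff are told to double the dose before looking at calcium.** The plan does not state an order.
- **That confirmed hypercalcemia would continue on 4000 IU/d.** The stop rule prevents that.
- **That a toxic level is in prospect.** The stepped-up study dose equals, and does not exceed, the 4000 IU/d limit cited in Potential Risks, and the projected 25(OH)D is unremarkable.

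**Conclusion.** The gap is real, narrow and minor. As written, the step-up depends on 25(OH)D alone, and a participant who also has a 4FV1 calcium above 10.6 mg/dL would be told to double the dose while the repeat is outstanding. The duration is bounded by the 14 days to the repeat draw plus an unstated turnaround, so the extra dose is at most 28,000 IU by day 14 and can be far less. The number affected cannot be derived from the documents; it is probably zero under the assumptions shown.

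It would be wrong to read this as a threat to the trial's results: endpoints, power and analysis are untouched. The change is worth making because a stated dosing rule gives the less safe action and the correction costs almost nothing.

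**What to change.** In both the 4FV1 paragraph and Vitamin D intervention, make the 2-pill instruction conditional on a 4FV1 calcium of 10.6 mg/dL or lower. If it is higher, keep the participant on 1 pill a day until the repeat is 10.6 mg/dL or lower, then step up. If hypercalcemia is confirmed, discontinue under Potential Risks item 4 as already written.

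Select and instruct the matched placebo participant only when the active step-up is actually issued, and apply the same calcium condition to that participant. This keeps the pairing intact and protects the blind.

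The calcium is already drawn and already checked by the same coordinator, so no new test is needed. The only downside is a later step-up for an affected participant: at most 14 to 19 days (with the assumed turnaround) out of 52 − 16 = 36 remaining weeks, or 252 days. That is 14/252 = 5.6% to 19/252 = 7.5% of the remaining time.
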